1. PROJECT TITLE

A Randomized, Subject-Masked, Active-Controlled, Parallel-Arm Clinical Trial Comparing Serratus Plane and Paravertebral Nerve Blocks

4. ESTIMATED DURATION OF THE STUDY

Three years (1 month preparation, 24 months enrollment, 11 months publication prior to closure)

5. LAY LANGUAGE SUMMARY OR SYNOPSIS (no more than one paragraph)

Following painful surgical procedures of the breast, postoperative analgesia is often provided with a paravertebral nerve block (PVB). For intense, but shorter-duration acute pain, a single-injection of local anesthetic is used with a duration of approximately 12 hours. Recently an alternative block has been reported: the serratus plane block.² The theoretical benefits include ease of administration since it is a plane superficial to the PVB and therefore easier to identify and target with ultrasound (therefore increasing success rate); and an increased safety margin as there are fewer anatomic structures in the immediate area which could be injured with the needle; and, the target plane is much further from the intrathecal/epidural space relative to the PVB, therefore leakage of cerebrospinal fluid or injury to the spinal cord are less likely with the serratus compared to the PVB.³ There are, therefore, multiple theoretical reasons to prefer the serratus over the PVB. Unfortunately, it remains unknown if the analgesia provided by this new technique is comparable to that provided with the PVB.⁴ We therefore propose to compare these two techniques with a randomized, subject-masked, active-controlled, parallel-arm clinical trial.

6. SPECIFIC AIMS

The overall objective of the proposed research is to determine the relative risks and benefits of serratus plane versus paravertebral blocks for single-injection local anesthetic administration.

Hypothesis 1: Following breast surgery, **analgesia** will be non-inferior in the recovery room with a serratus plane block compared with a paravertebral block as measured with the Numeric Rating Scale.

Hypothesis 2: For breast surgery, **opioid** consumption will be non-inferior in the operating and recovery rooms with a serratus plane block compared with a paravertebral block (primary: cumulative intravenous morphine equivalents).

Primary end point: *In order to claim that serratus plane blocks are non-inferior to paravertebral blocks, both Hypotheses 1 and 2 must be at least non-inferior.*

7. BACKGROUND AND SIGNIFICANCE

Following painful surgical procedures of the breast, postoperative analgesia is often provided with a

paravertebral nerve block (PVB). For intense, but shorter-duration acute pain, a single-injection of local anesthetic is used with a duration of approximately 12 hours. The PVB has several limitations: it can decrease blood pressure, and very rare—but serious—complications have occurred, including neuraxial injection, neuraxial hematoma, and pleural puncture.¹ An alternative block has been described: the serratus plane block.² The theoretical benefits include ease of administration since it is a plane superficial to the PVB and therefore easier to identify and target with ultrasound (therefore increasing success rate); and an increased safety margin: there are few anatomic structures in the immediate area which could be injured with the needle; and, the target plane is much further from the intrathecal/epidural space relative to the PVB. Lastly, the plane may be easier to catheterize for continuous peripheral nerve blocks relative to the relatively-small volume PVB.³

There are therefore multiple *theoretical* reasons to prefer the serratus plane block. Unfortunately, it remains unknown if the analgesia provided by this new technique is comparable to that provided with the PVB.⁴ We therefore propose to compare these two techniques with a randomized, subject-masked, active-controlled, parallel-arm, human subjects clinical trial.

8. PROGRESS REPORT

There are no preliminary or pilot study data.

9. RESEARCH DESIGN AND METHODS

This investigation will be a randomized, subject-masked, active-controlled parallel-arm, human subjects clinical trial. Of note, we will be using standard-of-care local anesthetic under an FDA-approved purpose and do not plan to research a possible change of indication or use of these medications as part of this research project. The treatments in both groups are currently used at our institution and there is true clinical equipoise at this time. The only difference in treatment between subjects who enroll versus those not enrolled in this study will be those who enroll will have the decision between which anatomic block location determined randomly, as opposed to the physician simply choosing him/herself.

Enrollment. Consenting adults undergoing breast surgery with a planned single-injection regional analgesic will be offered enrollment. Patients undergoing breast surgery with a planned perineural catheter regional analgesic will be excluded. Study inclusion will be proposed to eligible patients prior to surgery. If a patient desires study participation, written, informed consent will be obtained using a current UCSD IRB-approved ICF. Selection for inclusion will not be based on gender, race, or socioeconomic status. The study population of interest includes men and women of all races and socioeconomic status. Inclusion and exclusion criteria are listed in section #9 below.

Preoperative Procedures. Following written, informed consent, we will collect baseline anthropomorphic information (e.g., age, sex, height, and weight). All subjects will have a peripheral intravenous (IV) catheter inserted, standard noninvasive monitors applied, supplemental oxygen administered via a nasal cannula or face mask, and placed in the sitting position. Midazolam and fentanyl (IV) will be titrated for patient comfort, while ensuring that patients remain responsive to verbal cues. Both possible block locations will be viewed with ultrasound. If one or both of the locations is unacceptable for block placement in the clinician's opinion, the subject will not be randomized and will not proceed further with the study.

Subjects will then be randomized using a computer-generated list and opaque, sealed envelopes to

one of two treatment groups: (blocks of 4, stratified for unilateral vs. bilateral surgery): (1) serratus plane or (2) paravertebral block. All blocks will be placed by a regional anesthesia fellow or resident under the direct supervision and guidance of a regional anesthesia attending (or by the attending themselves).

The area of needle insertion will be cleaned with chlorhexidine gluconate and isopropyl alcohol. All blocks will be placed using standard UCSD ultrasound-guided techniques as previously described.^{2,3}

Ropivacaine 0.5% (20 mL for unilateral surgery; 16 mL each side for bilateral surgery) will be administered via the needle into the target plane(s). For PVBs without axillary involvement, this will be at the T3 and T5 levels. For PVBs with axillary involvement, this will be at the T2 and T4 levels. For unilateral PVBs, 10 mL of local anesthetic will be injected per level. For bilateral PVBs, 8 mL of local anesthetic will be injected per level.

Single-injection blocks will be considered successful if, within 30 minutes, the subject experiences decreased sensation to cold temperature with an alcohol pad over the approximate level of the ipsilateral 4th thoracic dermatome. Misplaced blocks will be replaced successfully, or the patient excluded from further study participation. For subjects undergoing bilateral surgical procedures, a block using the same protocol will be administered on the contralateral side.

Intraoperatively, all subjects will receive a general anesthetic using inhaled and intravenous anesthetic and oxygen. Intravenous fentanyl will be administered for cardiovascular responsiveness to noxious stimuli at the discretion of the anesthesia provider.

Postop: Subjects will be discharged with a prescription for oxycodone 5 mg tablets for supplementary analgesia and instructed to record the time at which they take their first opioid tablet as well as the time at which they believe the block starts to wear off.

Outcome measurements (end points). Pain scores will be recorded using the NRS. Within the recovery room, pain scores, opioid requirements, and antiemetic administration will be recorded by nursing staff masked to treatment group. The morning following surgery, all subjects will be contacted by phone or in person [if hospitalized] to record lowest, average, highest, and current pain scores; sleep disturbances, and nausea using a 0-10 Likert scale (0 = no nausea; 10 = vomiting). For outpatients, opioid requirements will be recorded while inpatients will have opioid requirements extracted from the electronic medical record. In addition, we will extract antiemetic use from the electronic record. We will collect the times at which subjects felt their block resolve and they consumed their first opioid analgesic pills following recovery room discharge.

Hypothesis 1: Following breast surgery, **analgesia** will be non-inferior in the recovery room with a serratus plane block compared with a paravertebral block as measured with the Numeric Rating Scale.

Hypothesis 2: For breast surgery, **opioid** consumption will be non-inferior in the operating and recovery rooms with a serratus plane block compared with a paravertebral block (primary: cumulative intravenous morphine equivalents).

Primary end point: *In order to claim that serratus plane blocks are non-inferior to paravertebral blocks, both Hypotheses 1 and 2 must be at least non-inferior.*

Statistical methods. Descriptive statistics will be provided by arm and in aggregate. Baseline characteristics of arms will be compared using the Wilcoxon-Mann-Whitney and Fisher's Exact tests. Key characteristics that are significantly different ($p<0.05$) will be included as covariates in the analysis models.

Primary aim. We will test the noninferiority of the serratus nerve block compared to the paravertebral nerve block. The 95% confidence interval (CI) associated with the Wilcoxon-Mann-Whitney test will be derived for the group difference (paravertebral minus serratus) in median pain scores within the recovery room. If the lower limit of the 95% CI is greater than -1.25, we will conclude noninferiority. If there are significant differences between the groups in any key characteristics, these characteristics will be included as covariates in a linear model. The same noninferiority margin (-1.25) will be applied to the 95% CI for the covariate adjusted group difference in mean pain derived from the linear model.

The noninferiority of the serratus nerve block with regard to total opioid consumption within the operating and recovery rooms will be tested in the same manner as pain, i.e. comparing the limits of a 95% CI associated with the Wilcoxon-Mann-Whitney test to a predefined noninferiority margin (in this case 2 mg). Covariate adjusted linear models will again be applied in the event that key characteristics are significantly different between the groups.

Sample size justification. Power for the Wilcoxon-Mann-Whitney derived noninferiority testing is based on 10,000 simulated trials. We simulated pain scores from a discrete distribution with median (interquartile range) 3 (2-5).⁵ Between the quartiles, the probability of each score was assumed constant. The distribution for each group was assumed to be the same. The sample size of $n=50$ per group provides 82% power to detect noninferiority in pain with a margin of 1.25. Similarly, opioid consumption was assumed to follow a truncated normal distribution with mean 2.5 mg and standard deviation 2 mg, and minimum value 0 mg. The sample size of $n = 50$ per group provides at least 95% power to detect noninferiority with margin 2 mg. Therefore, we will enroll 50 subjects for each of two treatments with primary end point values for a total enrollment of 100 subjects with a primary end point. To allow for dropouts, we request a maximum enrollment of 120 subjects. Noninferiority in pain is tested first, and if significant, noninferiority in opioid consumption is tested. Under this hierarchical testing framework, no adjustment in alpha is necessary to control Type 1 error.⁶

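### Randomisation is stratified by unilateral versus bilateral surgery, but neither primary Wilcoxon interval uses the stratum, so some power for pain may be given away

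*Combined protocol and SAP*

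**What the plan says.** All of the relevant text is in Section 9 (Research Design and Methods), apart from one line in Section 8.

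- **Randomisation:** a computer-generated list in "blocks of 4, stratified for unilateral vs. bilateral surgery". Laterality is the only stratification factor.
- **Pain:** "The 95% confidence interval (CI) associated with the Wilcoxon-Mann-Whitney test will be derived for the group difference (paravertebral minus serratus) in median pain scores". The decision rule is "If the lower limit of the 95% CI is greater than -1.25, we will conclude noninferiority".
- **Opioid consumption:** handled in the same way, by "comparing the limits of a 95% CI associated with the Wilcoxon-Mann-Whitney test to a predefined noninferiority margin", here 2 mg.
- **Covariates:** "Key characteristics that are significantly different ($p<0.05$) will be included as covariates in the analysis models". The opioid paragraph repeats the rule: "Covariate adjusted linear models will again be applied in the event that key characteristics are significantly different between the groups".
- **Sample size:** the simulation behind the stated power (82% for pain, at least 95% for opioids, 50 per group) describes no strata.
- **Section 8:** "There are no preliminary or pilot study data".

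The stratification factor does not appear in the analysis of either primary endpoint.

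**The concern.** Stratified randomisation improves precision only if the analysis knows about it. When the stratum predicts the outcome, balancing the arms on it removes that source of variation from the true error of the treatment comparison. An unstratified interval still counts the variation between strata as noise, so it comes out too wide.

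The covariate rule does not repair this. It selects factors by observed imbalance, and laterality is the one factor the design forces into balance. If some other characteristic does trigger the linear model, only the imbalanced characteristics enter, so laterality is still left out.

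What is at stake is power for pain. Pain has the lower stated power, it is tested first, and both hypotheses must succeed before noninferiority can be claimed.

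**Working it through.** **1. Can the covariate rule admit laterality?** Blocks of 4 limit the arm difference to 2 patients per stratum at randomisation. Two-sided Fisher tests with 50 per arm:

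| Bilateral cases | Split | Fisher p |
|---|---|---|
| 2 | 2 vs 0 (smallest attainable p) | 0.495 |
| 10 | 6 vs 4 (worst case) | 0.74 |
| 30 | 16 vs 14 (worst case) | 0.83 |
| 50 | 26 vs 24 (worst case) | 0.84 |

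Exclusions after randomisation could loosen the balance. At a 30% share, however, 19 vs 11 gives p=0.126 and 20 vs 10 is the first significant split (p=0.049). At a 50% share, 30 vs 20 gives 0.071 and 31 vs 19 gives 0.027. The rule would practically never bring laterality in.

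**2. Reproducing the stated power.** The protocol assumes a discrete pain score with median 3 and quartiles 2 and 5, evenly spread between quartiles and identical in both arms. Read as probability 1/12 each on 0-2, 1/4 on 3, 1/8 each on 4-5 and 1/20 each on 6-10:

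- mean = 3/12 + 3/4 + 9/8 + 40/20 = 4.125
- variance = 5/12 + 9/4 + 41/8 + 330/20 − 4.125² = 24.292 − 17.016 = 7.276, so SD = 2.70

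The one-sided 2.5% Wilcoxon test at shift 1.25 with 50 per arm has 81.0% power, against 82% stated. That is close enough to accept this reading. Putting the lowest quarter on 0-1 instead gives about 73%, which does not fit.

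**3. The stratified alternative.** The van Elteren statistic is Z = Σ[W_s − E(W_s)]/(N_s+1) ÷ √{Σ Var(W_s)/(N_s+1)²}. Here W_s is the mid-rank sum in stratum s, N_s is the stratum size, and the variance is tie-corrected. Noninferiority is concluded if Z at shift −1.25 exceeds 1.96.

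**4. Assumptions not in the protocol.** Bilateral share q is 10-50%, and the mean difference d between strata is 0-2 points on the pain scale. Laterality was assigned by a logistic function of the score, so the overall distribution stays as planned. There were 100 subjects in permuted blocks of 4 within stratum, and 200,000 trials per setting.

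Pain power, unstratified to stratified:

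| d (points) | q = 10% | q = 30% | q = 50% |
|---|---|---|---|
| 0 | 81.0% to 80.6% | 81.0% to 80.7% | 81.0% to 80.7% |
| 0.5 | 81.0% to 80.8% | 81.2% to 81.1% | 80.9% to 80.9% |
| 1 | 81.2% to 81.3% | 81.3% to 81.9% | 81.4% to 82.2% |
| 1.5 | not run | 81.8% to 83.6% | 81.9% to 84.0% |
| 2 | 81.6% to 83.1% | 82.2% to 85.4% | 82.7% to 86.3% |

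**5. Interval width.** A smaller simulation (2,500 trials per setting) gives these mean widths of the pain interval, unstratified vs stratified:

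| d (points) | q = 30% | q = 50% |
|---|---|---|
| 0 | 1.99 vs 2.01 | 2.00 vs 2.01 |
| 1 | 1.99 vs 1.97 | 1.99 vs 1.95 |
| 2 | 1.98 vs 1.86 | 2.00 vs 1.84 |

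As a rough check, the share of pain variance due to laterality is q(1−q)d²/7.276. At d = 2 and q = 0.3 this is 0.21 × 4/7.276 = 0.115, and √(1 − 0.115) = 0.94. The simulated ratio is 1.86/1.98 = 0.94.

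**6. Error rate.** The one-sided error of the unstratified test did not exceed 2.5% in any setting. At d = 2 its two-sided error at no difference was about 3.7-3.8% instead of 5%.

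**7. Opioids.** With a normal distribution (mean 2.5, SD 2) truncated at 0, a 2 mg margin, and stratum differences of 0-2 mg (10,000 trials), power is at least 99.9% with either test.

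**The case against.** The strongest reply is that nothing in the plan is invalid. The simulation in Section 9 powers exactly the unstratified test that Section 9 prespecifies. Any error is conservative, so it cannot produce a false noninferiority claim. Unstratified power does not fall as laterality becomes prognostic: it rises from 81.0% to 82.2-82.7% at 2 points with 30-50% bilateral cases. The loss is measured against a better test, not against what the plan promised. All of this stands.

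The gain also depends on unknown inputs. Up to a 1-point stratum difference, the change lies between −0.4 and +0.8 percentage points. Gains above 3 points need laterality to explain about 12-14% of pain variance, and nothing in the protocol supports an effect that large. Bilateral subjects are blocked on both sides, and stratification may have been meant simply to balance the arms on the different anaesthetic volumes used for unilateral and bilateral surgery. This also stands, and it limits how strongly the point can be pressed.

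It does not remove the point. The investigators chose laterality as their only stratification factor, the two strata differ in both surgery and block, and pain is the endpoint with less power to spare. Adopting the stratified test costs little, and the downside if laterality proves irrelevant is small.

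**Conclusion.** The concern holds as a modest efficiency point, not a validity failure. Neither primary interval uses the randomisation stratum, and the covariate rule practically cannot bring it in.

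If laterality predicts pain, the unstratified pain interval is too wide by an amount that depends on the assumed effect: about 1-2% at a 1-point difference between strata and 6-8% at 2 points, for 30-50% bilateral cases. Stratifying pays for itself once the difference reaches somewhere between 0.5 and 1 point. The opioid endpoint has practically nothing to gain.

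These sizes rest on assumed bilateral shares and stratum differences and on the reading of the pain distribution that reproduces the stated power to within about 1 percentage point. The change is worth making because it is cheap and fixes the role of the stratum before results are seen.

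**What to change.** In the statistical methods of Section 9:

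- Prespecify the primary analysis of both endpoints as stratified by unilateral/bilateral surgery. Use a van Elteren test with mid-ranks and a tie-corrected variance within stratum, and compare its inverted 95% shift interval with the existing margins (−1.25 for pain, 2 mg for opioids). Opioids are included for consistency, not for power.
- State the assumption of a common shift across strata, and report the stratum-specific differences descriptively.
- Include the stratum term in any linear model, whatever the baseline p-values.
- Re-run the power simulation with strata over a stated range of bilateral shares and stratum differences.

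The cost is a sentence or two and one simulation run. No extra data are needed, because laterality is known at randomisation. The statistical price is at most about 0.4 percentage points of pain power if laterality is not prognostic, plus the common-shift assumption.

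### Fixed, published blocks of 4 let a fully informed observer predict up to one third of allocations, just after a subjective eligibility decision

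*Combined protocol and SAP*

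**What the plan says.** All of the relevant design text is in section 9 (Research Design and Methods).

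- **Sequence.** Allocation is in "blocks of 4, stratified for unilateral vs. bilateral surgery". The section on statistical methods plans equal arms: "we will enroll 50 subjects for each of two treatments with primary end point values", with up to 120 enrolled to allow for dropouts.
- **Concealment.** "Subjects will then be randomized using a computer-generated list and opaque, sealed envelopes to" one of the two groups.
- **Eligibility decision before the envelope.** Both sites are first viewed with ultrasound. "If one or both of the locations is unacceptable for block placement in the clinician's opinion, the subject will not be randomized". No criterion for acceptability is given, and no record of the decision is required.
- **Operators.** "All blocks will be placed by a regional anesthesia fellow or resident under the direct supervision and guidance of a regional anesthesia attending". Attendings may also do the procedure alone. Whoever does it necessarily learns the allocation. Section 12 also lets regional anesthesia fellows obtain consent.
- **Masking.** The trial masks subjects, and section 9 masks the nurses who record recovery-room outcomes. Masking of the block team is not claimed.

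The documents do not say who holds or opens the envelopes, whether they are numbered in sequence, whether the block size is kept from enrolling clinicians, or whether patients excluded at the ultrasound look are logged.

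**The concern.** Opaque envelopes hide the next card, but they do not hide what follows from the earlier ones. Once two patients in a block of 4 have received the same treatment, the rest of that block is known, and the fourth allocation is always known. A patient judged unacceptable is never randomized and so, by inference, uses no envelope. The sequence therefore stays countable.

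If the clinician who judges acceptability can foresee the next allocation, that judgment can drift with it, without any bad faith. Section 14 itself recognizes that an attending might have chosen the block that randomization did not assign. The arms could then differ before treatment. Recovery-room masking cannot repair that. Nor can adjustment for baseline characteristics with p<0.05 where the reasons for selection are unmeasured. In a noninferiority trial, a bias in favour of the serratus block raises the chance of a false claim, and a bias against it lowers power.

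**Working it through.** The plan gives no figure for predictability, so there is none to reproduce.

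**Inputs.** From section 9: block size 4, equal allocation, two strata, pain margin 1.25, stated power 82%. Assumptions: q, the probability that the observer knows any one earlier allocation (position in the block known), and v, the shift in expected pain (NRS points) that selection produces, upward before one arm's card and downward before the other's.

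**1. Certain share, full knowledge.** Six balanced sequences are possible. Positions 1 and 2 are never certain. Position 3 is certain with probability 1/3 (the first two alike). Position 4 is always certain.

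Share = (0 + 0 + 1/3 + 1)/4 = 1/3 = 33.3%.

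Incomplete last blocks change this little: 32.0 of 100 allocations if the strata hold 50 and 50, and 38.7 of 120 (32%) if they hold 90 and 30.

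**2. Best guess, full knowledge.** The chances of a correct guess at positions 1 to 4 are 1/2, 2/3, 2/3 and 1.

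g = (1/2 + 2/3 + 2/3 + 1)/4 = 17/24 = 70.8%.

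**3. Certain share, partial knowledge.** Certainty needs the two like allocations both to be known, which has probability q². The share is therefore s = q²/3.

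**4. Bias from selection on certain cards.** A share s of each arm is affected, with opposite signs, so bias = 2vs. With v = 0.5 this equals s in NRS points.

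| q | Certain share s | Bias at v = 0.5 | Share of 1.25 margin |
|---|---|---|---|
| 1.00 | 33.3% | 0.33 | 27% |
| 0.90 | 27% | 0.27 | 22% |
| 0.75 | 19% | 0.19 | 15% |
| 0.50 | 8% | 0.08 | 7% |

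Bias is proportional to v: at v = 0.25 the range is 0.04 to 0.17.

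If a fully informed observer acted on every best guess, bias = 2v(2g − 1) = 2v × 0.417 = 0.83v, or 0.42 at v = 0.5.

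**5. What that bias would do (normal approximation).** Power of 82% at margin 1.25 implies a standard error of 1.25/(1.96 + 0.915) = 0.435. With the true difference at the margin, a bias b towards serratus gives a false-claim probability of 1 − Φ(1.96 − b/0.435). That is 11.6% at b = 0.33 and 3.9% at b = 0.08, against a nominal 2.5%.

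**6. After the change.** Enumeration of an equal mix of blocks of 4, 6 and 8, with the observer told where each block starts but not its size, gives 8.9% certain and a best guess of 68.1%. If block starts are not told, simulation gives about 2.4% certain and about 68%.

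- Certain cards only, v = 0.5: 2 × 0.5 × 0.089 = 0.09, down from 0.33.
- Every best guess, v = 0.5: 2 × 0.5 × (2 × 0.681 − 1) = 0.36, down from 0.42.

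Varying the size therefore removes most certain allocations but little of the guessing advantage.

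**The case against.** A reader might infer that the design makes one third of allocations certain in advance to the block team. The documents do not support that. One third is the ceiling for someone who knows the block size and the whole allocation history of both strata. Several operators are described, and nothing shows that any one of them has that history. That the clinician who judges acceptability also places the block is the natural reading, but it is not stated. This part of the objection stands, and it is why the result is given as a range over q.

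The value v = 0.5 has no source in the documents, and it may be hard to reach. As an illustration, assume normal selection, pain SD 2.0 to 2.7, and a correlation of 0.3 between what the clinician sees and later pain. Each shift would then require rejecting about 38% to 52% of the patients who present at certain cards. At a correlation of 0.5 it would be 21% to 30%. Rejection on that scale would be noticed if it were recorded, but the protocol requires no such record.

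The existing safeguards are real: sealed envelopes, acceptability judged before allocation and for both sites, masked subjects and masked recorders. Section 9 also states that the team is in equipoise. These reduce the risk, but none of them stops counting from past allocations.

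**Conclusion.** The vulnerability is real and its mechanism is in the text: a fixed, published block size, unmaskable operators, and an opinion-based exclusion directly before the envelope. Its size depends on knowledge that the documents do not describe. Up to 33.3% of allocations are certain with full knowledge, falling to about 8% if half of the earlier allocations are known. The matching bias is 0.33 down to 0.08 NRS points if v = 0.5, and proportionally less for smaller v. Both q and v are assumptions, and so is the direction of any bias.

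This is not evidence that selection has occurred, and it does not affect the sample size calculation. It is a weakness that is cheap to reduce and that the planned analysis could not correct afterwards, so the change is worth making.

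**What to change.** 1. For envelopes not yet used, regenerate the list with randomly varying block sizes within each stratum, for example 4, 6 and 8.
2. Move the block sizes out of the protocol into a file held by the statistician.
3. Keep the ultrasound check before the envelope, as now. Record the acceptability decision, with its reason, before the envelope is opened, and include patients who are not randomized.

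Items 2 and 3 are essential. Varied sizes bring certain allocations to at most about 9%, but best-guess accuracy only to about 68%, so item 1 alone leaves most of the guessing advantage in place.

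The cost is one new list, a short protocol change and one logged decision per patient, with no extra patients. The possible imbalance when enrollment stops mid-block rises to 4 per stratum (8 trial-wide), against 2 per stratum (4 trial-wide) with the present blocks.

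### Axillary involvement sets how the paravertebral block is given, but the plan does not require it to be recorded in both arms before allocation and adjusts for it only through a baseline test that would rarely fire

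*Combined protocol and SAP*

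**What the plan says.** All of this is in section 9, Research Design and Methods.

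- **Block delivery.** Two rules govern the paravertebral block: "For PVBs without axillary involvement, this will be at the T3 and T5 levels" and "For PVBs with axillary involvement, this will be at the T2 and T4 levels". The protocol states no axillary variant for the serratus block. It does not define axillary involvement or say when, or for which patients, it is determined.
- **Baseline data.** After consent, "we will collect baseline anthropomorphic information (e.g., age, sex, height, and weight"). These are examples, not a closed list; axillary status is not among them.
- **Allocation.** The scheme is "blocks of 4, stratified for unilateral vs. bilateral surgery". Axillary status is not a stratum.
- **Adjustment.** "Baseline characteristics of arms will be compared using the Wilcoxon-Mann-Whitney and Fisher's Exact tests", and then "Key characteristics that are significantly different ($p<0.05$) will be included as covariates in the analysis models". The key characteristics are not listed. The rule covers both pain and opioid consumption, and when triggered it brings in a linear model.
- **Decision rule for pain.** The difference is paravertebral minus serratus: "If the lower limit of the 95% CI is greater than -1.25, we will conclude noninferiority".

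No estimate by axillary status is planned, and the power simulation gives both arms one common pain distribution.

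**The concern.** The plan itself treats axillary involvement as important enough to change how the comparator block is given. It is reasonable to expect such a factor to be related to recovery-room pain and opioid use. Three things follow.

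1. If the arms differ by chance in the share of axillary cases, the estimated difference in that trial shifts. The only safeguard is a significance test on the imbalance, and a test with 50 per arm detects only large imbalances. The size of the shift depends on the imbalance and on how strongly axillary surgery affects the outcome, not on the p-value.
2. Precision available from a known factor is given up.
3. The serratus block might do worse specifically in axillary cases. Nothing planned would show this, and a pooled noninferiority result could sit on top of it. If status is written down only where it is needed to choose paravertebral levels, the comparison by axillary status is harder to make afterwards.

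**Working it through.** **Inputs from the plan:** 50 per arm; pain margin 1.25; two-sided 95% interval (one-sided 2.5%); "We simulated pain scores from a discrete distribution with median (interquartile range) 3 (2-5"); stated pain power 82%.

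**Assumptions, because the documents give no figures:** axillary prevalence 20-50%; axillary surgery adds 1-1.5 NRS points.

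**The plan's own figure.** SD from the interquartile range = (5 - 2)/1.349 = 2.22. SE of the difference = 2.22 × √(2/50) = 0.445. Power at no true difference = Φ(1.25/0.445 - 1.96) = Φ(0.85) = 80%. Simulating the rank-based interval, with a quarter of the probability on each of the scores 0-2, 3, 4-5 and 6-10, gives 80.1-80.6%. Other readings of the unstated tails give 73-94%. The stated 82% is reproduced closely enough to use this SD.

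**How often the p<0.05 rule acts.** Exact enumeration of two independent Binomial(50, prevalence) counts with Fisher's exact test:

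| Assumed prevalence | Arms differ by ≥10 points | Fisher p<0.05 | p<0.05, given ≥10 points |
|---|---|---|---|
| 20% | 26% | 2.8% | 11% |
| 30% | 33% | 3.1% | 9% |
| 40% | 36% | 3.2% | 9% |
| 50% | 37% | 3.5% | 10% |

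The rule therefore misses 89-91% of imbalances of 10 points or more. As an example, 20/50 v 30/50 gives p=0.071 (no adjustment) and 20/50 v 31/50 gives p=0.045 (adjustment).

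**Size of the shift.** Shift = imbalance × axillary effect. Smallest: 0.10 × 1 = 0.1. Largest: 0.20 × 1.5 = 0.3. Against the margin that is 0.1/1.25 = 8% to 0.3/1.25 = 24%.

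**Conditional effect on the decision.** With a true difference at the margin and an imbalance that favours serratus by s, false noninferiority = 1 - Φ(1.96 - s/0.445): 2.5% at s=0, 4.1% at 0.1, 6.5% at 0.2 and 9.9% at 0.3. With no true difference and an imbalance against serratus of 0.1, power = Φ((1.25 - 0.1)/0.445 - 1.96) = 73%, down from 80%. These figures describe trials in which the imbalance has already happened. Over all randomisations the error stays at 2.5%.

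**Gain from adjustment.** R² = effect² × p(1-p)/SD². With effect 1 and p=0.3: 0.21/4.95 = 4%. With effect 1.5 and p=0.5: 0.5625/4.95 = 11%. Interval width scales with √(1-R²), so it narrows by about 2-6%.

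**Effect modification.** Suppose serratus is 2 points worse in axillary patients only (assumed, and beyond the margin). The pooled difference is prevalence × 2, and SE² = [2 × 2.22² + p(1-p) × 2²]/50. At p=0.3 the pooled difference is 0.6, SE = 0.463, and noninferiority is declared with probability Φ((1.25 - 0.6)/0.463 - 1.96) = 29%. At prevalences of 20, 40 and 50% it is 46, 16 and 8%.

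**Precision of estimates in axillary patients.** Half-width = 1.96 × 2.22 × √(2/m). With m=15 per arm (30% prevalence) it is 1.6 NRS; with m=25 (50%) it is 1.2.

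**Opioid endpoint.** The documents give nothing from which to size an axillary effect, so no shift is computed. Simulated power under the plan's assumptions is above 99.9% (stated: at least 95%), so there is more room there.

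**The case against.** A reader might infer that axillary status is settled only after allocation, and only in paravertebral patients. The documents do not say so. They are silent, the baseline list is illustrative, both block sites are inspected in every subject before randomisation, and planned axillary surgery may well be known from the booking, from which it could be retrieved later. What stands is that nothing requires it to be recorded.

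A reader might also infer that the serratus block is never adapted. The protocol refers to standard techniques described in cited sources, so only the absence of a stated variant can be shown.

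It is tempting to say that imbalance goes uncorrected and inflates the error rate. Neither holds. The p<0.05 rule could bring axillary status in, and its weakness is common to any covariate chosen by a baseline test. The 4.1-9.9% figures are conditional, and only half of all imbalances favour serratus: 13-18% of trials have one of 10 points or more at prevalences of 20-50%. The 9.9% needs a 20-point favourable imbalance, which at prevalences of 30-50% arises in about 2-3% of trials, together with a 1.5-point effect. Removing the axillary variance from the conditional SE lowers it to about 9%.

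Finally, a stratum or main-effect covariate cannot correct a shortfall confined to axillary patients, and subgroup estimates will be imprecise: even with no true difference, subgroup noninferiority power is about 34-51% at 30-50% prevalence. The hypotheses concern breast surgery overall. This limits what reporting by axillary status can show, but it does not remove the case for recording it.

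**Conclusion.** The point holds as an inexpensive improvement in precision and reporting; it is not a flaw that invalidates the noninferiority test. The delivery rule depends on axillary status in one arm as written, and the plan has no requirement to record that status in both arms, no stratum, no named covariate and no estimate by axillary status. The fallback rule fires in about 3% of trials.

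Under the assumed 1-1.5 point effect, the consequence is a conditional shift in the pain difference of 0.1-0.3 and a forgone narrowing of the interval of about 2-6%. A different prevalence or effect would change these sizes. The documents do not support a claim of systematic bias or of an inflated overall error rate, nor a claim that serratus actually does worse in axillary cases; the latter is a possibility that the plan would not reveal. No view is taken on which injection levels are right.

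**What to change.** 1. Add one CRF field, planned axillary involvement (yes/no), taken from the surgical booking for every patient before the envelope is opened.
2. Prespecify it as a factor in both co-primary analyses regardless of any baseline p-value. Either use the linear model that the plan already provides for, or use a stratified Wilcoxon analysis with a Hodges-Lehmann interval, which keeps the primary method rank-based. Choose one before data are seen.
3. Report the pain and opioid differences separately for axillary and non-axillary patients, labelled descriptive, with intervals.

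A second randomisation stratum is optional and not needed.

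**Cost.** One field and a few sentences; the information is already needed to choose paravertebral levels, and no clinical procedure changes. There are two downsides. Planned and actual axillary surgery will sometimes differ, so the planned status must be the one analysed. The primary analysis also moves slightly away from the unadjusted Wilcoxon interval used in the power simulation, so the simulation should be rerun or the difference noted.
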